4.5 Registration to Correlative and Companion Studies

4.5.1 Registration to Substudies Described in Section 14.0

There are two substudies within Alliance A021602. The correlative studies must be offered to all patients enrolled on Alliance A021602 (although patients may opt to not participate). The substudies do not require separate IRB approval. The substudies included within Alliance A021602 are:

- Quality of Life Substudy, Alliance A021602-HO1 (Section 14.1)
- Population Pharmacokinetics Substudy, Alliance A021602-PP1 (Section 14.2)

If a patient answers "yes" to "I choose to take part in the Quality of Life study and will fill out the surveys," Question #1 in the model consent, then they have consented to participate in the substudy described in Section 14.1. The patient should be registered to Alliance A021602-HO1 at the same time they are registered to the treatment trial (A021602). Questionnaires should be submitted per Section 6.1.

If a patient answers "yes" to "I agree to have my blood collected, and I agree that my blood samples and related information may be used for the laboratory study described above," Question #2 in the model consent, then they have consented to participate in the substudy described in Section 14.2. The patient should be registered to Alliance A021602-PP1 at the same time they are registered to the treatment trial (A021602). Specimens should be submitted per Section 6.2.

4.6 Stratification and Grouping Factors and Treatment Assignments

Grouping Factors: Pancreatic NET vs. Carcinoid Tumor (i.e. non-pancreatic NET)

Randomization will be done separately within each cohort, pancreatic NET vs. carcinoid tumor.

Permuted Block

After a patient is registered, they will be assigned to one of the two treatment arms (cabozantinib vs. placebo) in a **2:1** ratio utilizing a permuted block schedule [37]. The goal of the algorithm is to maintain arm balance with respect to the following important stratification factors:

Stratification Factors for the Pancreatic NET Cohort:

- Concurrent Somatostatin Analog Use: Yes vs. No
- Prior Sunitinib Therapy: Yes vs. No

Stratification Factors for the Carcinoid Tumor Cohort:

- Concurrent Somatostatin Analog Use: Yes vs. No
- Primary Site: Midgut (jejunum, ileum, appendix, cecum, ascending, colon, hepatic flexure)/Unknown primary site vs. Non-midgut GI (stomach, duodenum, transverse colon, splenic flexure, descending colon, sigmoid colon, rectum)/Lung/Other known primary site not listed

When combined, these stratification factors create four stratum levels for each cohort, and each stratum level will have its own patient allocation schedule. The possible block size for this study is six.

4.7 Patient Re-Registration Requirements

Patient-completed Booklets: patient questionnaire booklets are to be ordered as outlined in Section 4.3.

Re-registration must occur \leq 28 days of local determination of disease progression.

4.8 Patient Re-Registration/Crossover (Step 2) Procedures

Patients who meet the criteria for centrally-confirmed radiologic disease progression will may be unblinded to treatment assignment. If the patient was on placebo, then they will be allowed to crossover to receive open-label cabozantinib provided that all criteria in Section 3.3 are met. If the patient was on cabozantinib, then the patient should be followed per Section 5.0.

Patients receiving placebo who choose to crossover and receive open-label cabozantinib must be registered to the cabozantinib arm of the study, as follows:

- 1) Log into OPEN registration system and select the appropriate patient.
- 2) Select the next registration step.
- 3) Complete OPEN Enrollment Form for the patient to change arms.
- 4) Enter Cycle # of the last treatment received on the placebo arm, on the OPEN Enrollment Form.
- 5) OPEN will determine eligibility for the patient to crossover to the new arm. If patient is not eligible, OPEN will indicate this.
- 6) Once the new arm assignment has been successfully completed, a confirmation email will be sent to the site staff.

Alliance A021602

7)	If assistance is needed with this	process, contact th	he Alliance Reg	istration	n Office a	ıt
Prior to	accessing OPEN, site staff sho	ald verify the follo	owing:			
•	Patient has met all re-regist	ration eligibility	criteria within	n the p	rotocol	stated

timeframes (see Section 3.3).

Note: The OPEN system will provide the site with a printable confirmation of re-registration and treatment information. Please print this confirmation for your records.

Access (OPEN at		o	r fro	om th	e OPEN	link on	the (CTSU	J membe	ers' websi	ite.
Further	instructional	information	is	in	the	OPEN	section	of	the	CTSU	website	at
					Fo	or any ac	dditional	que	stions	s, contac	et the CTS	SU
Heln De	sk at											

Open-label, patient-specific clinical supplies of cabozantinib will be shipped from the Pharmaceutical Management Branch (PMB) to the registering investigator at the time of patient re-registration and should arrive within 7 to 10 days of re-registration (see Section 10.1). Treatment is to begin within 14 days of re-registration.

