3.2.4 Patient History

No class III or IV CHF within 6 months of registration.

No clinically significant cardiac arrhythmia within 6 months of registration.

No unstable angina or MI within 6 months of registration.

No thromboembolic events within 6 months of registration (incl. stroke, TIA, DVT, & PE).

No known history of congenital long QT syndrome.

No uncontrolled hypertension within 14 days of registration (defined as SBP \ge 150 mmHg and/or DBP \ge 90 mmHg despite optimal medical management).

No clinically significant GI bleeding within 6 months of registration.

No clinically significant gastrointestinal abnormalities that may increase the risk for gastrointestinal bleeding within 6 months of registration including, but not limited to: active peptic ulcer, known endoluminal metastatic lesion(s) with history of bleeding, inflammatory bowel disease, or other gastrointestinal conditions with increased risk of perforation.

No GI perforation within 6 months of registration.

No known tumor with invasion into the GI tract from the outside causing increased risk of perforation or bleeding within 28 days of registration.

No radiologic or clinical evidence of pancreatitis.

No known cavitary lung lesions.

No known endobronchial lesions involving the main or lobar bronchi and/or lesions infiltrating major pulmonary vessels that increase the risk of pulmonary hemorrhage. (CT with contrast is recommended to evaluate such lesions.)

No hemoptysis greater than $\frac{1}{2}$ teaspoon (2.5 mL) or any other signs of pulmonary hemorrhage within the 3 months prior to registration.

No known tumor invading or encasing any major blood vessels.

No history of non-healing wounds or ulcers within 28 days of registration.

No history of fracture within 28 days of registration.

No brain metastases or cranial epidural disease unless adequately treated, stable, and off steroid support for at least 4 weeks prior to registration.

No known medical condition causing an inability to swallow oral formulations of agents.

No history of allergic reaction attributed to compounds of similar chemical or biological composition to cabozantinib/placebo.

No "currently active" second malignancy other than non-melanoma skin cancers or cervical carcinoma in situ. Patients are not considered to have a "currently active" malignancy if they have completed therapy and are free of disease for ≥ 3 years.

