3.2.7 Age \geq 18 years

3.2.8 ECOG Performance Status: 0-2

3.2.9 Required Initial Laboratory Values:

Absolute Neutrophil Count (ANC) $\geq 1,500/\text{mm}^3$

Hemoglobin $\geq 9 \text{ g/dL}$

Platelet Count $\geq 100,000/\text{mm}^3$

PT/INR, PTT < 1.3 x upper limit of normal (ULN)

AST/ALT $\leq 3 \text{ x ULN}$ Total Bilirubin $\leq 1.5 \text{ x ULN*}$

Creatinine ≤ 1.5 mg/dL **OR** Creatinine Clearance ≥ 45 mL/min

Albumin $\geq 2.8 \text{ g/dL}$

Potassium within normal limits (WNL)**

Phosphorus WNL**
Calcium WNL**
Magnesium WNL**

Urine Protein to Creatinine (UPC) Ratio ≤ 1

QTcF $\leq 500 \text{ msec}$ TSH WNL**

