3.3.1 Documentation of Disease

Patients must have centrally-confirmed radiographic disease progression per RECIST v1.1.

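### Crossover eligibility (Section 3.3) does not re-check ECOG 0-2 or the five tumor-location exclusions before a placebo patient's first cabozantinib

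*Combined protocol and SAP*

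**What the plan says.** **The crossover rule.** Section 4.8 lets a placebo patient cross over once progression is centrally confirmed. Its words are "then they will be allowed to crossover to receive open-label cabozantinib provided that all criteria in", and the list it then names is Section 3.3. It also directs sites to Section 3.3 before they use OPEN.

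**What Section 3.3 contains.** There are three items: progression (3.3.1: "Patients must have centrally-confirmed radiographic disease progression per RECIST v1.1"), not pregnant or nursing (3.3.2), and required laboratory values (3.3.3). The laboratory list matches 3.2.9, including UPC, QTcF and TSH. The re-registration summary at the front of the protocol gives the same list. Nothing in 3.3 refers back to 3.2.

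**What Step 1 requires in addition.** Performance status is limited by "3.2.8 ECOG Performance Status: 0-2". Section 3.2.4 has 21 statements, five of which are stand-alone exclusions by tumor location:

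- Bowel involvement: "No known tumor with invasion into the GI tract from the outside causing increased risk of perforation or bleeding within 28 days of registration"
- Central airways and lung vasculature: "No known endobronchial lesions involving the main or lobar bronchi and/or lesions infiltrating major pulmonary vessels that increase the risk of pulmonary hemorrhage"
- Large vessels elsewhere: "No known tumor invading or encasing any major blood vessels"
- Cavitation: "No known cavitary lung lesions"
- Central nervous system: "No brain metastases or cranial epidural disease unless adequately treated, stable, and off steroid support for at least 4 weeks prior to registration"

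**Treatment after crossover.** Section 7.1 starts open-label therapy at 60 mg daily, the same starting dose as blinded therapy.

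**The concern.** For a patient randomized to placebo, crossover is the first exposure to cabozantinib. The protocol considered the six items important enough to bar first exposure at Step 1, and two of the five location lines are worded by the bleeding or perforation risk they carry. The risk list in Section 9.4 names gastrointestinal perforation, fistula and hemorrhage, intracranial hemorrhage and respiratory hemorrhage.

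Step 2 is triggered by tumor growth. Growth can create a new location problem or worsen performance status, so having passed Step 1 does not settle the matter. A placebo patient whose progression scan shows vessel encasement or GI-tract invasion, or who is now ECOG 3, can still meet every written criterion for starting the drug. The stake is patient safety.

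**Working it through.** This is a comparison of text; the plan gives no figure to reproduce.

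**Step 1. Compare the two eligibility lists.**

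| Item | Step 1 (3.2) | Step 2 (3.3) |
|---|---|---|
| Pregnancy/nursing | 3.2.6 | 3.3.2, repeated |
| Laboratory values, UPC, QTcF, TSH | 3.2.9 | 3.3.3, repeated in full |
| ECOG 0-2 | 3.2.8 | absent |
| GI-tract invasion | 3.2.4 | absent |
| Cavitary lung lesion | 3.2.4 | absent |
| Main/lobar endobronchial or pulmonary-vessel lesion | 3.2.4 | absent |
| Major-vessel invasion or encasement | 3.2.4 | absent |
| Brain or epidural disease not treated and stable | 3.2.4 | absent |

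Of the six items at issue, 0 of 6 appear in 3.3.

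**Step 2. Look for a screen elsewhere between progression and first dose.**

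- 4.7 adds a time limit for re-registration (28 days from local progression) and no clinical condition.
- 5.0 schedules history, physical examination, performance status and CT at progression, and applies to crossover patients. No result bars re-registration. Brain imaging is not listed.
- 7.2.2 makes central review decisive for crossing over. The review is defined by RECIST 1.1 and confirmation of progression. Results go back to the site investigator for further evaluation, without thresholds.
- 8.1.7 only suggests monitoring for abdominal pain in patients with risk factors.
- 8.2 acts on adverse events once they occur. It has no rule for performance status or tumor location.
- 8.3 ends protocol therapy after emergency unblinding, which is unrelated to these conditions.
- 12.1.2 is permissive. 12.1.3 says a patient stopping for progression should cross over where applicable. Neither adds a clinical condition.
- 3.1 and 12.4 call for physician judgment, without thresholds.

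So 3.3 is the only clinical eligibility list for crossover, and nothing else sets a limit for the six items.

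**Step 3. Count the lines worded by risk.** The GI-invasion line refers to perforation or bleeding, and the endobronchial/pulmonary-vessel line to pulmonary hemorrhage. The cavitary, major-vessel and brain lines state no risk. That makes two of five.

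**Step 4. Bound the number who can reach the gate.** Section 13.2 plans 61 placebo patients in the pancreatic NET cohort and 69 in the carcinoid cohort: 61 + 69 = 130. This is a ceiling. Not every placebo patient will progress and choose to cross over, and Section 1.3 dates crossover from Update #02.

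**The case against.** The best defense is that this is the sponsor's choice. The sponsor repeated the laboratory block and left the history block out, and no passage requires first-exposure criteria to be applied twice. The six items function as entry criteria throughout: 8.2 would not stop a cabozantinib-arm patient who became ECOG 3 without RECIST progression. Four of the five location lines concern only known disease, so Step 1 also relies on what the investigator already knows, and at crossover the investigator has the performance status, examination and scan. Further text narrows the gap. The site investigator evaluates the central result (7.2.2). Symptomatic deterioration alone does not open unblinding (8.3.2). A patient who needs radiation leaves protocol therapy (8.1.10). Anticoagulation is barred with brain metastases (8.1.14). Therapy must stop if the protocol's constraints harm the patient (12.4). Finally, tightening the gate withholds active drug where Section 1.4 says there is no standard treatment.

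Part of this stands. The omission is a design choice, not a contradiction, and a reader might infer that nothing protects these patients. The documents do not support that: investigator judgment applies, and every crossover patient met Step 1 earlier. But the passages cited are general judgment or on-treatment rules, and none is a threshold at re-registration. The judgment clause in 3.1 applied equally at Step 1, where the sponsor still wrote explicit exclusions and allowed no waivers (3.0). No reason is given why judgment alone should suffice for first exposure after progression.

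**Conclusion.** The point holds as a safety gap in eligibility and should be fixed. Section 3.3 re-screens laboratory values, QTcF and pregnancy, but none of the six items that progression can newly change. At most 130 placebo patients could reach the gate. The number who would have one of the conditions cannot be derived, since the documents give no rate for any of them. That progression can produce these conditions is a clinical inference, not a statement in the protocol.

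Four stronger readings are tempting and are not supported:

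- *That the whole of 3.2.4 should be repeated.* The recent-event look-backs, blood-pressure limit and surgery intervals are largely handled by 8.2 once treatment starts, and the choice between entry and on-treatment standards there is the sponsor's.
- *That an adverse event between the last blinded dose and the first open-label dose escapes 8.2.* Its discontinuation rules, read with the Day 1 assessment in 5.0, largely cover this, so a separate pre-dose confirmation is not needed.
- *That all five location lines are framed by bleeding or perforation risk.* Only two are.
- *That the primary result is compromised.* The gate operates after centrally confirmed progression; PFS type I error and power are unaffected.

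**What to change.** Add to Section 3.3, the front-page re-registration summary and the Step 2 OPEN checklist:

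- (a) ECOG 0-2 at the progression visit.
- (b) The five tumor-location exclusions of 3.2.4, worded as they are now with time windows counted from re-registration. They should be judged on the progression scan and clinical information already obtained. The brain/epidural item should rest on known disease, with no new brain imaging.

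If the sponsor prefers a looser standard for crossover than for entry, 3.3 should say so and give the reason.

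The cost is amendment wording and six checklist items. The visit and scan at progression already exist, so no test is added. The downside is that a few placebo patients without a standard alternative would not qualify for open-label cabozantinib; their number cannot be derived.

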5.0 STUDY CALENDAR

The pre-study testing intervals are guidelines only. Laboratory and clinical parameters during treatment are to be followed using individual institutional guidelines and the best clinical judgment of the responsible physician. It is expected that patients on this study will be cared for by oncology providers experienced in the treatment and supportive care of patients on this trial.

Pre-Study Testing Intervals:

To be completed ≤ 14 DAYS before registration: All laboratory studies, history and physical To be completed ≤ 28 DAYS before registration: Any X-ray or scan of any type which is utilized for tumor measurement per protocol

**Calendar should be followed for both blinded therapy and for cross over patients. Crossover patients WILL NOT complete the Quality of Life and Pharmacokentic substudies. Re-registration should occur \le 28 days of local determination of disease progression while receiving blinded therapy with central confirmation of progressive disease.

	Prior to Registration*	Day 1 of each cycle*	Day 15 of Cycles 1 and 2 (+/- 3 days)	At progression or cessation of protocol treatment**
Tests & Observations				
History and Physical, PS	X	X	X	X
Pulse, BP, Height, Weight	X(1)	X(1)	X(1)	
ECG	X	A		
Adverse Event Assessment – CTCAE	X	X	X	В
Adverse Event Assessment – PRO-CTCAE	X(2)	X(2)		X(2)
Patient Medication Diary		X(3)		
Registration Fatigue/Uniscale Assessment	X(4)			
Laboratory Studies			***************************************	.
CBC w/ Differential, Platelets	X	X	X	
PT/INR, PTT	X			
Serum Creatinine	X	X	X	
Albumin, ALT, AST, Alk. Phos., Bilirubin	X	X	X	
Electrolytes (incl. Ca, Cl, CO2, K, Na, Mg, P), Glucose	X	X	X	
TSH	X	С		
Serum or Urine HCG	X(5)			
Urine Protein and Creatinine	X	D		
Serum Chromogranin A	X	С		
Hormone Assessment	Е	Е		
Staging				
CT Chest/Abd/Pelvis (or equiv.)	F	F		F
Real-time Central Review				X(6)
For patients who consent to pa	rticipate in A0216	б 02-НО1, А021 602	2-PP1, and A02160	02 Biobanking:
Quality of Life Substudy ⁷	0	•	(+/- 1 week) (i.e. nticancer therapy;	

Pharmacokinetic Substudy ⁷	Submission of plasma specimens on Day 1 of Cycles 1, 2, and 3 and on Day 15 of Cycles 1 and 2; see Section 6.2 , Section 14.2 .
	Submission of specimens within 28 days of registration, Cycle 1 Day 1, Cycle 2 Day 1, and at the time of progression; see Section 6.2

- * Labs completed prior to registration may be used for Day 1 of Cycle 1 tests if obtained ≤ 14 days prior to treatment. For subsequent cycles, all labs, scans, tests, and observations may be obtained +/- 3 days of scheduled clinic visit. Labs completed prior to re-registration must be completed ≤ 28 days.
- ** If protocol therapy is discontinued for reasons other than disease progression, physical examination, performance status, and radiologic imaging studies should be performed every 12 weeks (+/- 1 week) until disease progression or start of new anticancer therapy, whichever comes first. Patients who discontinue study treatment due to disease progression (or who start a new anticancer therapy after discontinuing study treatment for reasons other than disease progression) should be followed every 6 months for survival until 8 years after registration. See Section 12.0.
- Height only collected at baseline; weight only measured at baseline, on Day 1 of Cycles 1, 2, and 3, and on Day 15 of Cycles 1 and 2.
- Patients complete PRO-CTCAE by paper booklet ordered through the CTSU website. See Section 4.3 and Section 4.7 for ordering instructions. See Section 9.1 for administration instructions. See Appendix I for PRO-CTCAE assessments for IRB submission and review only. PRO-CTCAE booklets should be administered at the following time points: ≤ 21 days prior to treatment, Day 1 of every cycle, and at the time of progression (or cessation of protocol treatment). PRO-CTCAE should not be collected after patients crossover.
- The diary must begin the day the patient starts taking the medication and must be completed per protocol and returned to the treating institution (or compliance must be documented in the medical record by any member of the care team). See Appendix II.
- 4 To be completed after registration but ≤ 21 days prior to treatment.
- 5 For women of childbearing potential, see Section 3.2.6; must be done ≤ 14 days prior to registration and reregistration.
- Restaging scan documenting progressive disease while on blinded therapy must be submitted for real-time central review within 24 hours of local determination; see Section 6.3 and Section 7.2.2 for instructions regarding imaging submission and IROC notification of cases when there is a local determination of progressive disease and request for real-time central review.
- 7. Crossover patients will not participate in the Quality of Life or the Pharmacokentic substudies.
- A To be performed at baseline, on Day 1 of Cycle 2, and on Day 1 of Cycle 3.
- B Any adverse events that occur within 30 days of discontinuation of study treatment should be recorded in the last treatment cycle form.
- C To be performed at baseline, and then every 12 weeks (+/- 1 week) (i.e. every 3 cycles). Any measurements of biochemical response should occur in conjunction with the radiographic assessments for disease status.
- D To be performed every other cycle (i.e. Cycle 1, Cycle 3, Cycle 5, etc.).
- For patients with a history of carcinoid syndrome only: perform 24-hour urine 5-HIAA at baseline and then every 12 weeks (+/- 1 week) (i.e. every 3 cycles). Other hormones, such as gastrin, insulin, glucagon, and VIP should be assessed, if clinically indicated, at baseline and then every 12 weeks (+/- 1 week) if elevated. Any measurements of biochemical response should occur in conjunction with the radiographic assessments for disease status. For patients with functional neuroendocrine tumors (i.e. patients with symptoms related to hormone production) only: perform hormone assessment, if clinically indicated, at baseline and then every 12 weeks (+/- 1 week) if elevated.
- Baseline scans and scans within the 12 months prior to registration used to determine progression for eligibility should be submitted within 3 days; see Section 3.2.1, Section 6.3, and Section 7.2.3. Restaging scans will be performed after every 12 weeks (+/- 1 week) (i.e. every 3 cycles) until evidence of progression; restaging scan used for local determination of progression while on blinded therapy must be submitted for real-time central review within 24 hours; see Section 6.3 and Section 7.2.2.

Multiphase CT scan (chest/abdomen/pelvis) is the preferred imaging modality. Equivalent modalities (MRI scan of the abd/pelvis with either CXR or non-contrast chest CT) may be used at the discretion of the treating physician. The CT component of a PET-CT is also acceptable if the CT is of diagnostic quality (using oral and IV contrast). The same imaging modality used at baseline should be used for all subsequent evaluations. CT scans should be of diagnostic quality and performed with oral and IV contrast unless there is a medical contraindication. MRI scans should be of diagnostic quality and performed with IV contrast unless there is a medical contraindication. MRI is the preferred imaging modality for patients with a medical contraindication to contrast. See Section 7.2.1 for further details. Octreotide scan or Gallium-68-Dotatate scans cannot be used for tumor measurements. Supporting documentation is to be submitted per Section 6.1.1. Imaging and reports are to be submitted per Section 6.3.

